SGC	Salivary gland cancer
SPC	Summary of Product Characteristics (in Dutch: officiële productinfomatie IB1-tekst)
Sponsor	The sponsor is the party that commissions the organisation or performance of the research, for example a pharmaceutical company, academic hospital, scientific organisation or investigator. A party that provides funding for a study but does not commission it is not regarded as the sponsor, but referred to as a subsidising party.
SUSAR	Suspected Unexpected Serious Adverse Reaction
Wbp	Personal Data Protection Act (in Dutch: Wet Bescherming Persoonsgevens)
WMO	Medical Research Involving Human Subjects Act (in Dutch: Wet Medisch-wetenschappelijk Onderzoek met Mensen)

SUMMARY

Rationale: Salivary gland cancer (SGC) is a rare cancer with 24 histological subtypes. Treatment options for locally advanced and/or metastatic SGC are limited. The tyrosine kinase inhibitor cabozantinib suppresses tumor growth, angiogenesis, and metastasis, and has been approved for renal cell carcinoma and thyroid cancer. Cabozantinib may also be of value in advanced SGC because c-MET, one of the targets of cabozantinib, is frequently overexpressed in SGC.

Objectives: To assess the objective response rate (ORR), progression free survival (PFS), overall survival (OS), duration of response (DoR), toxicity, and quality of life (QoL) of patients with advanced SGC treated with cabozantinib in 3 cohorts: salivary duct carcinoma (SDC), adenoid cystic carcinoma (ACC), other SGC's.

Study design: Single arm, single center, phase II clinical trial

Study population: Patient with c-MET positive, locally advanced, recurrent, and/or metastatic SGC.

Intervention: Cabozantinib tablets 60 mg once daily until progressive disease, intolerable toxicity, or investigator and/or patient decision to withdraw for a maximum duration of 2 years.

Main study parameters/endpoints: study endpoints are in line with the objectives.

Nature and extent of the burden and risks associated with participation, benefit and group relatedness:

Burden and risks: Patients will use the study medication for a maximum duration of 2 years. During these 2 years, patients will make 17 study related visits. 12 CT scans will be made and patients will be asked to fill in questionnaires 7 times. The safety of Cabometyx is well known because of studies in renal cell carcinoma.

Benefit: Because Cabometyx has not been tested in SGC patients before, the chance of responding to treatment is unknown. The Simon 2-stage design will be used to prevent exposure of too many patients to ineffective treatment without discarding a potential effective treatment because of treatment failure in some patients.

Group relatedness: The study does not involve minors and/or incapacitated subjects.

1. INTRODUCTION AND RATIONALE

SGC is a rare cancer. The annual incidence rate ranges from 0.4-2.6 cases per 100,000 people. Besides, SGC's are histological diverse. Twenty-four histological types can be distinguished.¹ Primary treatment consists of resection of the affected salivary gland and a neck dissection, mostly followed by postoperative radiotherapy. Treatment options for patients with locally recurrent and/or metastatic disease (later: advanced disease) systemic treatment options are limited to androgen deprivation therapy (ADT) and HER2-targeted therapies in selected cases. Chemotherapy may be used for palliation, but the effect is limited. Therefore, new treatment options for advanced SGC are urgently warranted.

Cabozantinib is an oral, small-molecule inhibitor of tyrosine kinases, including c-MET, VEGFR, and AXL. In preclinical models, cabozantinib has been shown to suppress tumor growth, angiogenesis, and metastasis.² In clinical practice, it has been approved for treatment of advanced renal cell carcinoma in patients who received prior anti-angiogenic therapy (cabometyx® tablets),³ and treatment of progressive, metastatic medullary thyroid cancer (Cometriq® capsules).⁴ Next to this, it has shown promising results in bone metastases of castration-resistant prostate cancer.⁵

Cabozantinib may also be of value in the treatment of advanced SGC because c-MET, one of the targets of cabozantinib, is frequently overexpressed in SGC. In ACC, c-MET overexpression has been shown in 53.2% of patients.⁶ In SDC, c-MET overexpression has been shown in 39.7% of patients.⁷

No data are available on the efficacy of cabozantinib in SGC. We will conduct a phase II, single arm clinical trial to investigate the efficacy of cabozantinib in c-MET positive SGC. Three patient groups will be included: (1) advanced SDC, (2) advanced ACC, and (3) advanced SGC of other subtypes. As ACC can originate in the salivary glands, but also in other parts of the body, such as lung, trachea, breast and cervix, these patients can also be included in the study and will be analyzed in the cohort with advanced ACC patients.

Before and during treatment we will collect blood samples for future analysis of circulating tumor DNA (ctDNA). ctDNA is cell-free DNA in the blood circulation which originates from the tumor. Analysis of ctDNA may be of value for early response prediction. In colorectal cancer, treatment response and failure can be predicted by a decrease and increase of ctDNA.⁸ In this study, we will draw blood for ctDNA analysis using Roche cell-free DNA tubes before start of treatment, after 2 weeks, after 4 weeks, and before every evaluation CT-scan. Samples will be analyzed for ctDNA levels to evaluate whether treatment response and failure can be predicted.

2. OBJECTIVES

Objectives will be analyzed separately in all 3 cohorts of c-MET positive, advanced SGC: (1) SDC, (2) ACC originated in the salivary glands or other sites of the body, (3) other SGC's

Primary Objective

- Assess the ORR. ORR is defined as the sum of the complete remissions plus partial responses.⁹ The best response will be used in each patient.

Secondary Objectives

- Assess the PFS. PFS will be defined as time from study enrollment until disease progression or death.
- Assess the OS. OS will be defined as time from study enrollment until date of death of any cause.
- Assess the DoR. DoR is defined as time from study enrollment until date of documented tumor progression or death
- Assess the toxicity of cabozantinib. Toxicity will be scored according to NCI CTC common criteria v 4.0.¹⁰
- Assess the QoL of patients treated with cabozantinib using EORTC questionnaires.
- Assess the response rate by using continuous tumor shrinkage end-points, as was advocated by Billingham et al¹¹ and Wason et al.¹²
- ctDNA will be assessed to evaluate whether response and disease progression can be predicted.

More details about the definitions and analysis of primary and secondary outcomes are described in chapter 8.1.

3. STUDY DESIGN

Design: single arm, single center, phase II clinical trial

Duration: inclusion is expected to take approximately two years

Setting: single center study (Radboud University Medical Center, Nijmegen, the Netherlands)

Assessments

During the study patients will be seen every 2 weeks for the first 8 weeks, then every 4 weeks for the first 6 months, then every 8 weeks in the first year, and every 12 weeks in the second year. The following assessments will be done:

	History / physical exam	Blood analysis	CtDNA	Urine	ECG	Imaging	Questionnaires	Toxicity	Any other
	1	2	3	4	5	6	7	8	9
Week 0	X	X	X	X	X	X	X		X
Week 2	X	X	X	X	X			X	X
Week 4	X	X	X					X	X
Week 6	X	X						X	X
Week 8	X	X	X			X	X	X	X
Week 12	X	X						X	X
Week 16	X	X	X			X	X	X	X
Week 20	X	X						X	X
Week 24	X	X	X			X	X	X	X
Week 32	X	X	X			X		X	X
Week 40	X	X	X			X	X	X	X
Week 48	X	X	X			X		X	X
Week 56	X	X	X			X	X	X	X
Week 68	X	X	X			X		X	X
Week 80	X	X	X			X		X	X
Week 92	X	X	X			X		X	X
Week 104	X	X	X			X		X	X
At PD	X	X	X			X	X	X	X

1. History / physical exam
 - Standard history and physical examination
2. Blood analysis
 - Hematology: haemoglobin, blood cell count (RBC, WBC count and differential, platelets)
 - Biochemistry: AST, ALT, AP, GGT, LD, bilirubin, creatinine, urea, Na, K, Ca, P, Mg, albumin, . TSH and free T4 in week 0.
3. ctDNA
 - blood sample for ctDNA analysis
4. Urine
 - protein/creatinine ratio

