4.2 Inclusion criteria

In order to be eligible to participate in this study, a patient must meet all of the following criteria:

- Disease specific
 - locally advanced, recurrent, and/or metastatic SGC (excluding sarcomas and mesenchymal tumors)
 - c-MET positive disease (see paragraph 4.1)
 - Measurable disease per RECIST version 1.1
 - Cohort-specific criteria
 - SDC cohort:
 - Direct inclusion (no objective tumor growth prior to inclusion needed)
 - ACC cohort:
 - Inclusion after objective growth in the last three months or complaints due to the disease
 - Other SGC's
 - Inclusion after objective growth in the last three months or complaints due to the disease
- General conditions
 - Age \geq 18 years
 - Eastern Cooperative Oncology Group performance status of 0 or 1.
 - Normal number of neutrophils and thrombocytes
 - Liver function:
 - ALT and AST $<$ 2.5 x upper limit of normal (ULN)
 - Total bilirubin \leq 1.5 x ULN (except for Gilbert's syndrome)
 - Serum albumin \geq 28 g/L
 - Renal function:
 - Creatinine $<$ 1.5 x ULN or calculated creatinine clearance \geq 40 ml/min
 - Urine protein/creatinine ratio \leq 113.1 mg/mmol (\leq 1 mg/mg) or 24-hour urine protein $<$ 1 g
 - Hemoglobin A1c (HbA1c) \leq 8% or a fasting serum glucose \leq 9 mmol/l

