8.2 Secondary study parameters/endpoints (if applicable)

- Assess the PFS
 - PFS is defined as time from study enrollment until disease progression or death.
 - Outcome will be scored as 'progressed' or 'censored' according to the FDA guidance for industry of clinical trial endpoints.⁹
- Assess the OS
 - OS is defined as time from study enrollment until date of death of any cause.
 - Analysis of OS will be done at the end of the study (study related follow-up will be until 3 years after start of treatment)
- Assess the DoR
 - DoR is defined as time from study enrollment until date of documented tumor progression or death
 - Only patients with a CR or PR will be included in the assessment of DoR.
- Assess the toxicity of cabozantinib in SGC patients
 - Toxicity will be scored according to NCI CTC common criteria v 4.0.
- Assess the QoL of SGC patients treated with cabozantinib
 - QoL will be assessed using the EORTC QLQ-C30, EORTC QLQ-H&N35, PSSHN and VAS questionnaires.
- Assess the response rate of patients with advanced SGC treated with cabozantinib by using continuous tumor shrinkage end-points, as was advocated by Billingham et al¹¹ and Wason et al.¹²
- ctDNA will be assessed to evaluate whether treatment response and disease progression can be predicted.

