8.4 Study procedures

In chapter 3 (study design) we describe which assessments will be done and when. Below we describe what this means for a patient who decides to participate: how many study related visits will be made, how much blood will be drawn, how much radiation will be used etcetera.

- Treatment
 - A patient will use Cabometyx tablets once daily for a maximum of 2 years
- OPD visits
 - A patient will visit the OPD at week 0 (baseline), 2, 4, 6, 8, 12, 16, 20, 24, 32, 40, 48, 56, 68, 80, 92, 104 if he/she is on treatment for the maximum duration of 2 years. This means 17 planned study related visits in 2 years.
- Laboratory tests
 - Blood will be drawn by venapuncture at every visit.
 - At every visit, the following blood will be drawn:
 - First tube is always discarded → 3 ml tube
 - Hematology → 3 ml EDTA tube
 - Biochemistry → 3 ml lithium-heparin tube
 - ctDNA → 3x 8.5 ml Roche cell free DNA tubes
 - total: 34.5 ml of blood per visit
- Urine analysis
 - A urine portion will be analyzed for protein/creatinine ratio before start of treatment, after 2 weeks, and when clinically indicated.
- ECG
 - An ECG will be made before start of treatment, after 2 weeks, and when clinically indicated.
- Imaging
 - A neck-, chest-, and abdominal CT scan will be made in week 0, 8, 16, 24, 32, 40, 48, 56, 68, 80, 92 and week 104 if a patient stay on treatment during the maximum of 2 years. So 12 CT-scans of approximately 15 mSv will be made, resulting in a yearly exposure of 90 mSv. Taking the terminal disease into account, this corresponds to a effective dose in healthy adults of 9 mSv, which is a moderate risk. In our opinion, this exposure is justified concerning the relevance of the study. See the radiation ethic form for further details.
- Questionnaires
 - Questionairres will be taken 7 times (at baseline, week 8, week 16, week 24, week 40, week 56 and at PD)
 - The follow questionnaires will be taken:
 - EORTC QLQ-C30: 30 questions
 - EORTC QLQ-H&N35: 35 questions
 - PSSHN¹⁶: 3 questions
 - VAS: 1 question
 - Total: 30+35+3+1=69 questions

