e. Analysis of potential effect

Because cabozantinib has not been studied in SGC before, potential efficacy can't be predicted. The Simon 2-stage design will be used to minimize exposure of patients to this treatment in case of low-activity.

f. Pharmacokinetic considerations

Following oral administration of cabozantinib capsules or tablets, T_{max} ranged from 2 to 5 hour post-dose. The terminal half-life (for predicting drug washout) is approximately 120

hour. Repeat daily dosing of cabozantinib capsules at 140 mg for 19 days resulted in a 4- to 5-fold higher mean cabozantinib accumulation (based on AUC) compared with a single dose administration; steady state was achieved by Day 15. Cabozantinib is highly protein bound in human plasma ($\geq 99.7\%$).

A PopPK analysis of cabozantinib was performed using data collected from 289 cabozantinib-treated subjects with solid tumors following oral administration of 140-mg capsule daily doses. The predicted effective half-life for that formulation at that dose was approximately 55 h, V/F is approximately 349 L, and CL/F at steady-state was estimated to be 4.4 L/h. This PopPK analysis did not identify clinically relevant differences in clearance of cabozantinib between females and males or between Whites (89%) and non-Whites (11% [$<4\%$ were Asian]). Cabozantinib PK was not affected by age (20-86 years).

More information about the pharmacokinetics can be found in paragraph 5.2 of the IB.

g. Study population

The study population are patients with locally advanced and/or metastatic SGC. This is a life-threatening condition and at the moment of inclusion the condition is unstable, because SDC is an aggressive tumor and for the others types of SGC objective growth is needed prior to inclusion. Next to this, treatment options are very limited in this situation (see introduction). Women with child bearing potential could be included in the study, but have to take contraceptive measures in order to participate.

h. Interaction with other products

In summary, currently available data suggest that cabozantinib: (1) is not anticipated to markedly induce or inhibit CYP enzymes at clinically-relevant plasma concentrations; (2) is a substrate for CYP3A4; (3) may have the potential to inhibit the P-gp transport activity but is not a substrate of P-gp; and (4) is a substrate of drug-transporter MRP2. More information can be found in paragraph 6.4 of the IB.

i. Predictability of effect

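### No thyroid test is scheduled on treatment and no urine protein test after week 2, so the toxicity endpoint does not systematically ascertain silent thyroid change or proteinuria

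*Combined protocol and SAP*

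**What the plan says.** Section 8.2 makes toxicity a secondary endpoint: "Toxicity will be scored according to NCI CTC common criteria v 4.0". Section 10.2 will summarise it by simple descriptive statistics and names no denominator. Under 9.2.1, adverse events enter the record when the patient reports them or staff observe them.

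The laboratory schedule is in chapter 3 and section 8.4:

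- **Thyroid.** The only entry is "TSH and free T4 in week 0".
- **Urine protein.** Section 8.4 states: "A urine portion will be analyzed for protein/creatinine ratio before start of treatment, after 2 weeks, and when clinically indicated". In the chapter 3 table the week-2 row ("Week 2 X X X X X X X") is the last with a mark in the urine column. The row for progressive disease has none.
- **Blood panel.** It is "Biochemistry: AST, ALT, AP, GGT, LD, bilirubin, creatinine, urea, Na, K, Ca, P, Mg, albumin". Section 8.4 adds: "Blood will be drawn by venapuncture at every visit".
- **Discretionary tests.** Column 9 of the table, marked at every visit, lets the investigator add any test judged necessary.

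Section 4.2 sets entry limits for the urine protein/creatinine ratio and for glycaemia (HbA1c at most 8% or fasting glucose at most 9 mmol/l). A urine test is listed at week 0. Neither HbA1c nor glucose is listed there.

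**The concern.** A laboratory abnormality without symptoms can be graded only if somebody measures it. The plan takes a thyroid baseline but schedules no later value to set against it. It uses urine protein as an entry limit, rechecks it once at two weeks, and then leaves it to clinical indication for the rest of treatment. A change that gives no symptoms is unlikely to prompt that indication, and it is neither reported by the patient nor seen by staff until a test is done.

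What is at stake is how the toxicity table will be read. If the rates of thyroid abnormality and proteinuria are given over all treated patients, nobody can tell an event that was absent from one that was not looked for. The trial is described as the first use of this drug in this disease, so its toxicity table is likely to be cited.

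A smaller point concerns documentation: an entry criterion on glycaemia has no matching test in the week-0 list.

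**Working it through.** **Visit count.** The plan's own figure is 17 visits in two years (section 8.4). The weeks listed are 0, 2, 4, 6, 8, 12, 16, 20, 24, 32, 40, 48, 56, 68, 80, 92 and 104, which is 17, so the figure reproduces. On-treatment visits: 17 − 1 = 16.

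**Scheduled on-treatment samples for a patient treated for the full 104 weeks** (chapter 3 table and lists, section 8.4):

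| Test | Scheduled on treatment | Last scheduled |
|---|---|---|
| TSH / free T4 | 0 of 16 | week 0 |
| Urine protein/creatinine ratio | 1 of 16 | week 2 |
| Creatinine, urea, electrolytes, albumin | 16 of 16, and at progression | week 104 |
| HbA1c or glucose | none listed, week 0 included | – |

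Weeks with no scheduled urine test still to come: 104 − 2 = 102, and 102/104 = 98%. The longest gap between creatinine samples is 12 weeks (for example week 56 to week 68). Patients who stop earlier have fewer weeks of exposure, but the thyroid count stays at 0 and the urine count at no more than 1.

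**Direction of the bias.** Let π be the true proportion of patients with a silent abnormality, and t the probability that such a patient is tested while it is present. The expected proportion reported over all treated patients is π × t. With complete scheduled testing t approaches 1. With discretionary testing t is at most 1 and depends on what prompts a test, so the reported figure is at most π. The documents give neither π nor t, so only the direction follows, not the amount.

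If the denominator is instead the number tested, the reader can see how much ascertainment there was. That proportion may still be unrepresentative, because patients tested for cause differ from the rest. Reporting the number tested makes the gap visible; only scheduled tests close it.

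**Effect on the primary analysis.** None. The rule (0 of 9, then more than 2 of 17) gives an exact type I error of 0.0466 and power of 0.812 at a 25% response rate, which match the stated 0.047 and 0.81. No laboratory toxicity enters that calculation.

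**The case against.** The other side has a good deal to say.

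- **Renal toxicity is monitored.** A reader might infer that silent renal toxicity cannot be graded. That is wrong: creatinine and urea are drawn at every on-treatment visit, so a symptomless fall in renal function would be seen. The gap is proteinuria alone.
- **Later testing is allowed.** Section 8.4 permits urine tests on clinical indication, and column 9 permits any other test at any visit. These routes mean that the events can be graded in patients who are tested. They do not give systematic ascertainment, because each needs a trigger or a decision.
- **Importance is not shown.** The frequent and serious reactions listed in 11.4 include neither thyroid dysfunction nor proteinuria. Management of adverse events is referred to the Investigator's Brochure, which is not available here and might contain further monitoring. This stands, and it limits how strongly the point can be put.
- **Fatigue.** A reader might argue that fatigue (56% in 11.4) could not be separated from thyroid dysfunction. But fatigue is a symptom, and a symptom is what the discretionary routes respond to.
- **Timing of the week-2 sample.** A reader might argue from 13.1 ("steady state was achieved by Day 15") that week 2 comes before full exposure. Those data are from 140 mg capsules, whereas section 5.1 specifies tablets starting at 60 mg. The argument is not needed: one value at two weeks says little about up to two years on any pharmacokinetics.
- **Glycaemia.** A reader might infer that a patient above the limit could be enrolled unnoticed. The documents do not show this. Criteria are reviewed at the start of the baseline visit (11.2), and the value may come from routine care. The chapter 3 table is not a full eligibility work-up either, since c-MET testing is not in it. The printed panel also has a stray comma and full stop after albumin, so an item may have been lost from the list.

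**Conclusion.** The point holds in a limited form. As scheduled, the secondary toxicity endpoint does not systematically ascertain symptomless thyroid change (0 of 16 on-treatment visits) or proteinuria after week 2 (nothing scheduled in 102 of up to 104 weeks). The reported rates would depend on who was tested and would tend to be underestimates.

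This assumes that the chapter 3 table and section 8.4 are the complete schedule, and that no mandatory monitoring is set out in the Investigator's Brochure. The amount of underestimation is unknown. The consequence is confined to a descriptive secondary endpoint. It is worth correcting because the correction is cheap, not because it threatens the trial's main conclusion.

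The glycaemic criterion is a possible gap in the listing, to be confirmed by the sponsor, and no more than that.

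**What to change.** 1. In the chapter 3 table and section 8.4, add on-treatment TSH/free T4 and the urine protein/creatinine ratio, for ascertainment of the toxicity endpoint, at visits that are already planned. The sponsor should choose which; the imaging visits are one option.
2. In 10.2, state that thyroid abnormalities and proteinuria will be reported with the number of patients tested on treatment as denominator, beside the number treated.
3. If no tests are added, say in 10.2 and in the report that these toxicities were not systematically ascertained.
4. Reconcile the HbA1c/fasting glucose criterion in 4.2 with the week-0 list, and state where the value comes from.

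**Cost.** No new visit is needed. Blood is drawn at every visit, and 8.4 lists the same tubes for every visit, with none extra for the week-0 thyroid tests. The laboratory should confirm that those tubes suffice. The additions are the thyroid assays, a urine portion at the chosen visits, and a somewhat higher reported toxicity rate, because silent events would now be counted.

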5. ECG
 - Standard ECG
6. Imaging
 - CT- or MR-scanning of primary tumor area and regional lymph nodes
 - Chest plus abdominal CT
 - *An independent endpoint review committee will be installed to verify responses according to RECIST version 1.1.¹³*
7. Questionnaires:
 - EORTC QLQ-C30
 - EORTC QLQ-H&N35
 - PSSHN
 - VAS
8. Toxicity
 - Toxicity profile according to NCI CTC common criteria v 4.0
9. Any other
 - Any other diagnostic procedure that the investigator deems necessary

